8.10.2. Tables over the whole 24 weeks period

Tables will present the imputed 4 treatment groups up to Week 12, and leave out the placebo group after Week 12, as mentioned in section 2.1.1. Same analysis as for the DAS28(CRP). Population: ITT. Note that the SF-36 is only scored at baseline, Week 4, Week 12, and Week 24/EDV. LOCF and observed case (descriptive only at baseline, week 12 and week 24). Tables will present the 8 domain scores and the 2 main scores.

Table 14.2.1.10.1:SF-36: Descriptive statistics of the actual values

Table 14.2.1.10.2:SF-36: Descriptive statistics of the change from baseline

Table 14.2.1.10.3:SF-36: Descriptive statistics of the percent change from baseline

(descriptive statistics, and a frequency table at weeks 12 + 24)

Table 14.2.1.10.4:SF-36: Summary with overall p-value and pairwise comparisons versus placebo**Table 14.2.1.10.5:SF-36: Exploratory pairwise comparisons among the dose groups****8.10.3. Figures over the whole 24 weeks period**

Line plots showing baseline, Week 4, 12 and 24. Same analysis as for the DAS28(CRP). Population: ITT. LOCF only. Both main scores as well as the 8 subdomains will be presented.

Figure 14.2.1.10.1: SF-36: Plot of the actual values over time**Figure 14.2.1.10.2: SF-36: Plot of the changes from baseline over time****Figure 14.2.1.10.3: SF-36: Plot of the percent changes from baseline over time****8.10.4. Tables after Week 12**

Tables will present Weeks 4, 12 and 24, unless specified otherwise, for the 8 arms of “efficacy chapter 3”. The same descriptive analysis as DAS28(CRP) will be performed. Analysis population: ITT. LOCF and observed case (weeks 12 + 24 only). Tables will present the 8 domain scores and the 2 main scores.

Table 14.2.1.10.6: SF-36 after Week 12: Descriptive statistics of the actual values**Table 14.2.1.10.7: SF-36 after Week 12: Descriptive statistics of the change from baseline****Table 14.2.1.10.8: SF-36 after Week 12: Descriptive statistics of the percent change from baseline****8.10.5. Figures after Week 12**

No figures planned.

8.10.6. Listings**Listing 16.2.6.10: SF-36: Derived summary scores**

Listing per treatment group, per subject and per time point of all derived summary scores (the 2 component scores and the 8 domain scores): actual values, changes from baseline and percent changes from baseline.

Population: ITT.

9. DEFINITIONS OF PHARMACOKINETICS TABLES, LISTINGS AND FIGURES

These analyses will be described in a separate SAP. A separate report will be written based on the analysis performed by [REDACTED].

10. DEFINITIONS OF PHARMACODYNAMICS TABLES, LISTINGS AND FIGURES

Mock tables, listings and figures are provided in a separate document.

All analyses will be run on the ITT population, unless specified otherwise.

10.1. PARAMETERS

Assessment: marker YKL-40 (also known as Chitinase 3 L 1, CHI3L1) in serum.

Visits to present:

- Baseline
- Week 12: this is either the Week 12 visit itself, OR the EDV visit in case the subject dropped out of the study prior to Week 12, OR the last post-baseline visit prior to Week 12.

The actual values, changes from baseline and percent changes from baseline will be derived and analyzed.

Note that the percentage change from baseline remains missing if the baseline value itself equals zero.

10.2. TABLES

Tables will present Baseline and Week 12, unless specified otherwise. Tables will present the 4 treatment groups.

Analysis population: ITT.

Table 14.2.3.1: Pharmacodynamics: YKL-40: Descriptive statistics

Descriptive statistics of actual values, changes from baseline and percent changes from baseline.

Table 14.2.3.2: Pharmacodynamics: YKL-40: Summary with overall p-value and pairwise comparisons versus placebo

Analysis model is similar to DAS28(CRP). Only one time point: Week 12.

Table 14.2.3.3: Pharmacodynamics: YKL-40: Descriptive statistics for Week 12 ACR20 responders versus non-responders

Same as previous table, but split up for Week 12 ACR20 responders and non-responders.

Table 14.2.3.4: Pharmacodynamics: YKL-40: Descriptive statistics for Week 12 ACR50 responders versus non-responders

Table 14.2.3.5: Pharmacodynamics: YKL-40: Descriptive statistics for Week 12 ACR70 responders versus non-responders

Table 14.2.3.6: Pharmacodynamics: YKL-40: Exploratory pairwise comparisons among the dose groups

Table 14.2.3.7: Pharmacodynamics: YKL-40: Correlation with ACR20/50/70

Relationship between the change from baseline in PD marker and ACR20 will be investigated via a logistic regression model on the ACR20 responses, with the following factors in the model: treatment groups, baseline YKL-40, change from baseline in YKL-40. ACR20 and YKL-40 will be taken from the same visit.

Same for the ACR50 and ACR70.

Table 14.2.3.8: Pharmacodynamics: YKL-40: Correlation with continuous efficacy parameters

Relationship between the change from baseline in PD marker and the change from baseline in efficacy parameters will be investigated via Pearson's correlation coefficient as provided by SAS PROC CORR. Efficacy parameters and YKL-40 will all be taken from the same visit. The following efficacy parameters will be tested:

- ACR20 components: TJC68, SJC66, the 3 VAS scores, CRP and HAQ-DI.
- Summary scores: DAS28(CRP), CDAI and SDAI.

10.3. FIGURES

Figure 14.2.3.1: Pharmacodynamics: YKL-40: Mean plot over time

Line plot baseline-W12, like for the efficacy parameters. Plot will contain the 4 groups.

Analysis population: ITT.

Figure 14.2.3.2: Pharmacodynamics: YKL-40: Correlation plots versus efficacy

Correlation scatterplots of the percent changes from baseline in YKL-40 versus:

- Percent change from baseline in: TJC68, SJC66, the 3 VAS scores, CRP and HAQ-DI
- Percent change from baseline in DAS28(CRP), CDAI, and SDAI

Efficacy parameters and YKL-40 will all be taken from the same visit. Each plot on a new page, using different plot symbols per group.

Analysis population: ITT.

10.4. LISTINGS

Listing 16.2.8: Pharmacodynamics: YKL-40

Listing per treatment group, per subject and per time point of the YKL-40 results: actual values, changes from baseline and percent changes from baseline.

Population: ITT.

11. DEFINITIONS OF PK/PD TABLES, LISTINGS AND FIGURES

These analyses will be described in a separate SAP. A separate report will be written based on the analysis performed by [REDACTED].

12. DEFINITIONS OF SAFETY TABLES, LISTINGS AND FIGURES

Mock tables, listings and figures are provided in a separate document.

All analyses will be run on the Safety population, unless specified otherwise.

12.1. ADVERSE EVENTS

12.1.1. Treatment-Emergent Principle

All adverse events with onset on or after first dosing are considered treatment-emergent adverse events (TEAE).

Adverse events will be placed into analysis periods according to their start date. Analysis periods: see section 3.2. The AE will only be presented in the analysis period during which it started. Rule: period start date \leq AE start date \leq period stop date.

In case the AE start date is incomplete, a worst-case allocation will be done according to the available parts of the AE start date. When too much of the AE start date is missing to apply the above rules, the AE will be allocated to:

- the first treatment period, in case the doubt is between the screening and first treatment analysis period;
- both treatment periods, in case the doubt is between both treatment periods.

All adverse events emerging during the screening period will only be listed, not presented in any of the tables. These events are not TEAEs. All tables will present TEAEs only.

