3. ANALYSIS PERIODS AND ANALYSIS TIME POINTS

3.1. RELATIVE NUMBER OF DAYS

The relative day (DY) is calculated as follows:

= Visit date – reference date + 1 day, when the visit date is on or after the reference date

= Visit date – reference date, when the visit date is before the reference date.

The reference date in the study is the first study medication intake date, which by definition has DY=1. There is no DY=0.

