4.4. HANDLING MISSING DATA

4.4.1. Handling of Missing Date (Time) or Partially Known Date (Time)

No imputation will be done of missing date (time) fields, nor of the missing parts of partially known date (time) fields. When needed, a worst-case selection will be made. Such worst-case selection rules are elaborated in the specific sections (e.g., AE).

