7.7.1. Classification of Therapies

All prior and concomitant therapies will be allocated into exactly one of the following categories (using the analysis periods as defined in section 3.2):

- Prior only: the therapy ended before the first study treatment administration.
- Concomitant only: the therapy started on or after the first study drug administration.
- Post-treatment: the therapy started after the last study drug administration.
- Prior and concomitant: the therapy started before the first study drug administration, and ended on or after the first study drug administration.

When the start date is completely missing, the therapy is assumed to have started on the same day as the first administration of study medication.

When the end date is missing, the therapy is assumed to be still ongoing after the end of the study.

When the start date is only partially known, the missing parts will be imputed by the first day of the month/year, or the day of the first medication intake in case the nonmissing part matches.

When the end date is only partially known, the missing parts will be imputed by the last day of the month/year, or the day of the last medication intake in case the nonmissing part matches.

Imputation of start and end dates is only done for the classification into prior / concomitant / prior + concomitant. The listing will present the original start and end dates, also when incomplete. Fields like start and stop days will not be derived from imputed incomplete dates.

The relative study day of therapy start and stop will be derived as follows (only listed):

Start day

= (Therapy start date) – (date of first study medication administration) + 1, when the start date of therapy is known and complete, and when the therapy start date is on or after the date of first study medication;

= (Therapy start date) – (date of first study medication administration), when the start date of therapy is known and complete, and when the therapy start date is before the date of first study medication;

= missing when the start date of therapy is unknown, missing, or incomplete.

Stop day

= (Therapy stop date) – (date of first study medication administration) + 1, when the end date of therapy is known and complete, and the end date of therapy is on or after the date of first study medication;

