12.1.4. Adverse Event Onset Day and Duration

AE onset day in the study

= (AE start date) – (date of first study drug administration) + 1, when the AE start date is completely known;

= missing when the AE start date is incomplete or unknown.

AE onset day in the period

= (AE start date) – (start date of the period into which the AE was allocated) + 1, when the AE start date is completely known;

= missing when the AE start date is incomplete or unknown.

AE duration

= (AE stop date) – (AE start date) + 1, when both dates are completely known;

= (trial termination date) – (AE start date) + 1, when the AE start date is fully known but the AE is not resolved at the end of the study; in this case the duration will be presented as ">x days" in the listing to identify it as a censored result;

= missing when the AE start date is incomplete or unknown, or when the AE has resolved but with an incomplete or unknown end date.

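### Adverse events with an incomplete start date are allocated to periods without using the stop date, so events known to have ended before first dose or by Week 12 can be miscounted; the effect is small

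*SAP*

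**What the plan says.** **Allocation.** SAP 12.1.1 defines a treatment-emergent event as one with onset on or after first dosing. "Adverse events will be placed into analysis periods according to their start date", and each event is shown only in the period in which it began. For an incomplete start date, "a worst-case allocation will be done according to the available parts of the AE start date". If too much of that date is missing, the event goes to "the first treatment period, in case the doubt is between the screening and first treatment analysis period", or to "both treatment periods, in case the doubt is between both treatment periods". SAP 4.4.1 rules out imputing partial dates and leaves the worst-case rule to sections such as this one.

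**Period boundaries.** Under SAP 3.2, screening ends the day before first dose. The first 12 weeks run up to and including the Week 12 visit date, and the second 12 weeks begin the next day. SAP 12.1.7 plans adverse event tables for the first 12, second 12 and full 24 weeks.

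**Use of the stop date.** The event's stop date enters the duration in SAP 12.1.4 and is printed in Listing 16.2.10.1. For therapies, SAP 7.7.1 does classify by end date: "Prior only: the therapy ended before the first study treatment administration".

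**Onset day.** SAP 12.1.4 gives the onset day in the study as start date minus first-dose date plus 1, or "missing when the AE start date is incomplete or unknown". It has no separate branch for events before first dose. SAP 3.1 adds 1 only on or after the reference date and states "There is no DY=0".

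**The concern.** A stop date is an upper bound on onset. If an event is known to have resolved before first dose, onset on treatment is impossible whatever part of the start date is missing. The same holds for onset in the second 12 weeks when the event resolved on or before the Week 12 visit. A worst-case rule is meant for real uncertainty. Here it can act where recorded data have removed the uncertainty, and the result departs from the section's own onset definition.

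Pre-dose events are to be expected. Events are recorded from signature of consent (Protocol 8.7.1.4.1.2), Screening lasts up to 28 days, and subjects taking methotrexate are washed out of it then (Protocol 8.6.1.1). What is at stake is the accuracy of the safety tables: the treatment-emergent counts by randomised arm, and the tables for the second 12 weeks.

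**Working it through.** The plan states no figure that depends on this rule, so there is none to reproduce. The check applies the written rule to dated cases and then sizes the effect under assumptions.

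**1. The rule with and without the stop date.** Assume first dose on 10 June 2014. Day 85, the target Week 12 visit, is then 2 September 2014, and the second 12 weeks begin on 3 September.

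| Start date recorded | Stop date | Rule as written | Onset limited by stop date |
|---|---|---|---|
| June 2014, day unknown | 5 June | Possible dates 1 to 30 June: screening or first 12 weeks, so first 12 weeks (treatment-emergent) | Possible dates 1 to 5 June: screening only |
| September 2014, day unknown | 1 September | Possible dates 1 to 30 September: both treatment periods | Possible date 1 September: first 12 weeks only |

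For a placebo subject, or a 50 mg non-responder moved to 100 mg, the extra count in the second row falls in the 100 mg period before any 100 mg dose was given. For a subject who stays on one dose, the extra count is in the wrong period but under the right dose.

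**2. Size of the pre-dose error.** The documents give only the 280 subjects, 70 per arm (Protocol 8.5.4). Everything else is assumed:

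- pre-dose events per subject: 0.2, 0.3 or 0.5;
- share with an incomplete start date: 2%, 5% or 10%;
- share of those resolved before first dose, with a stop date that shows it: one half;
- share with first dose in the same calendar month as onset. With only the day missing, an onset in an earlier month is plainly screening and raises no doubt.

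For the last factor, take the day of the month of first dose, d, as uniform on 1 to 30, and onset as uniform over the 28 days before. For a given d, min(d − 1, 28) of the 28 onset days share the month. Summing over d gives (0 + 1 + … + 28) + 28 = 406 + 28 = 434, out of 30 × 28 = 840, or 0.517.

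False treatment-emergent events = 280 × events per subject × incomplete share × 0.5 × 0.517:

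| Assumption | Before the month factor | After |
|---|---|---|
| Low: 0.2, 2% | 280 × 0.2 × 0.02 × 0.5 = 0.56 | 0.3 |
| Middle: 0.3, 5% | 280 × 0.3 × 0.05 × 0.5 = 2.1 | 1.1 |
| High: 0.5, 10% | 280 × 0.5 × 0.10 × 0.5 = 7.0 | 3.6 |

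Spread over four arms, the high case is 3.6 / 4 = 0.9 events per arm. One misplaced subject in an arm of 70 is 1/70 = 1.4 percentage points on the affected row. Double counts at Week 12 cannot be sized from the documents.

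**3. Onset day.** Take an event that starts the day before first dose, which is the Baseline visit, Day -1 in Protocol 8.6.1.2. SAP 12.1.4 gives (−1) + 1 = 0. SAP 3.1 gives −1, and a therapy started that day is Day −1 under SAP 7.7.1. Any pre-treatment event with a complete start date is shifted by one day in the same way. The field is carried into Listing 16.2.10.2, which repeats the details of Listing 16.2.10.1.

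**The case against.** **The fallback needs doubt.** Both fallback bullets apply only where there is doubt between two periods, and the section says screening events are not treatment-emergent. A careful programmer could hold that a stop date before first dose leaves no doubt. That is fair, and the mock tables, which are a separate document, might settle it. So the text permits the miscount and does not state it outright. But the rule ties allocation to the parts of the start date that are available and never mentions the stop date. No other section of the SAP adds that condition.

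**The therapy rule is a different concept.** Therapies are classified by overlap with treatment, so their end date is intrinsic. Events are classified by onset. This stands: SAP 7.7.1 shows that end dates, including partial ones, can be used in this way. It does not show that the SAP contradicts itself.

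**Such cases will be rare.** Missing and inconsistent data are queried (Protocol 8.9.3), subjects record new events on a diary card (Protocol 8.5.10), and events are reviewed at each treatment-period visit. The tables count subjects, so a false event need not change the number with at least one event. Listing 16.2.10.1 prints period and event dates on one line, so the error can be seen. All of this stands and supports a small effect.

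**The rule is declared worst case and is the same in every arm.** True, and it is conservative for total counts. It is not neutral in every table: a false event on placebo narrows the contrast with active arms, and a false second-period event in a switched subject falls in the 100 mg period.

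**Conclusion.** The point holds as a small gap in specification. Under SAP 12.1.1 as written, an event with an incomplete start date can be tabulated as treatment-emergent although it ended before first dose. It can also be counted in the second 12 weeks although it ended on or before the Week 12 visit. Under the assumed rates the first error produces about 0.3 to 4 false events over all 280 subjects; the second is unquantified. The primary endpoint and all other efficacy results are untouched.

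A reader might infer three stronger things that the documents do not support:

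- **That these events are all charged to active drug.** A pre-dose event enters whichever arm was randomised, including placebo. The extra second-period count falls on a dose not yet given only for subjects who switched.
- **That treatment-emergent counts are materially inflated.** No rates are given, and the assumed ones yield at most about one false event per arm.
- **That the onset-day formula distorts the tables.** It contradicts SAP 3.1, but it changes listings only.

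**What to change.** **SAP 12.1.1.** State that the set of possible onset dates is first limited to dates that agree with the available parts of the start date and are not later than the stop date. For a partial stop date, use its latest possible date. If all remaining dates lie in one analysis period, the event is allocated to that period (screening if all precede first dose). The worst-case rule applies only if more than one period remains possible.

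This is better written as one rule on possible dates than as separate stop-date cut-offs at first dose and at Week 12. Separate cut-offs overlap, because a stop before first dose is also a stop before Week 12. A cut-off at Week 12 alone could also move an event with clear screening onset into the first treatment period.

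**SAP 12.1.4.** Use the two-branch formula of SAP 3.1 for the onset day in the study.

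**Cost.** A short text change and a few lines of programming on dates already collected. No new data are needed.

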12.1.2. Treatment Relatedness

Following (ICH-E3), the investigator's assessment of drug relatedness will be dichotomized as follows:

Drug related: at least possibly drug related, OR with missing drug relatedness (= worst-case)

Not drug related: less than possibly drug related.

In tabulations this dichotomized parameter will be used, but in the listings the original parameter will be presented. Note that there is only the drug-relatedness assessment by the investigator.

12.1.3. Worst-Case Principle

When cross-tabulating AE preferred terms versus an AE attribute (e.g., intensity), the worst-case is always applied within each analysis period. I.e., when a subject has two times the same AE preferred term in the same analysis period, then the subject is reported only once: only with the worst intensity. If this happens in two different analysis periods, the AE is reported twice: once in each analysis period.

12.1.4. Adverse Event Onset Day and Duration

AE onset day in the study

= (AE start date) – (date of first study drug administration) + 1, when the AE start date is completely known;

= missing when the AE start date is incomplete or unknown.

AE onset day in the period

= (AE start date) – (start date of the period into which the AE was allocated) + 1, when the AE start date is completely known;

= missing when the AE start date is incomplete or unknown.

AE duration

= (AE stop date) – (AE start date) + 1, when both dates are completely known;

= (trial termination date) – (AE start date) + 1, when the AE start date is fully known but the AE is not resolved at the end of the study; in this case the duration will be presented as ">x days" in the listing to identify it as a censored result;

= missing when the AE start date is incomplete or unknown, or when the AE has resolved but with an incomplete or unknown end date.

12.1.5. Calculation of Percentages

All percentages will be calculated against the total number of subjects that are still in the study in that particular analysis period.

12.1.6. Tables up to Week 12

No formal inferential statistics (p-values) will be derived.

An as-treated analysis will be performed. All tabulations and listings will present treatments rather than analysis periods.

Table 14.3.1.1: Treatment-emergent adverse events up to Week 12: Summary table

Tabulation per treatment of the number and percentage of subjects with the following:

- Subjects with at least one treatment-emergent adverse event (TEAE)
- Subjects with at least one serious TEAE
- Subjects who died (treatment-emergent)
- Subjects with at least one mild TEAE as worst intensity
- Subjects with at least one moderate TEAE as worst intensity
- Subjects with at least one severe TEAE
- Subjects with at least one TEAE that was considered treatment-related
- Subjects with at least one treatment-emergent SAE that was considered treatment-related
- Subjects with at least one TEAE for which the study treatment was temporarily stopped
- Subjects with at least one TEAE for which the study treatment was permanently stopped
- Subjects with at least one TEAE flagged as an individual stopping criterion by the investigator.

Population: safety.

Table to be created for the Week 12 interim analysis as well.

Table 14.3.1.2: Treatment-emergent adverse events up to Week 12: Summary table by region

Same table as the preceding one, but by geographical region.

Population: safety.

Table 14.3.1.3: Treatment-emergent adverse events up to Week 12: Tabulation of all adverse events

Tabulation of TEAE preferred terms per body class, per treatment group.

Population: safety.

Table to be created for the Week 12 interim analysis as well.

Table 14.3.1.4: Treatment-emergent adverse events up to Week 12: Tabulation of all adverse events by region

Same as previous table, but split up by geographical region.

Population: safety.

Table 14.3.1.5: Treatment-emergent adverse events up to Week 12: Tabulation of all adverse events by gender

Same as previous table, but split up for males and females.

Population: safety.

Table 14.3.1.6: Treatment-emergent adverse events up to Week 12: Tabulation of all adverse events by age category

Same as previous table, but split up for age categories:

< 45 ;

[45,65[;

[65,75[;

≥ 75 years.

Population: safety.

Table 14.3.1.7: Treatment-emergent adverse events up to Week 12: Tabulation per intensity

Cross-tabulation of TEAE preferred terms versus their intensity. Use the worst-case intensity per TEAE per subject. Per treatment group.

Population: safety.

Table to be created for the Week 12 interim analysis as well.

Table 14.3.1.8: Treatment-emergent adverse events up to Week 12: Tabulation of all treatment-related events

Tabulation of TEAE preferred terms per body class, per treatment group. Selecting only the TEAEs that were treatment-related (see section 12.1.2).).

Population: safety.

Table to be created for the Week 12 interim analysis as well.

Table 14.3.1.9: Treatment-emergent adverse events up to Week 12: Tabulation of all treatment-related events by gender**Table 14.3.1.10: Treatment-emergent adverse events up to Week 12: Tabulation of all treatment-related events by age category**

Table 14.3.1.11: Treatment-emergent adverse events up to Week 12: Tabulation of the intensity of treatment-related events

Cross-tabulation of TEAE preferred terms versus their intensity; per body class and per treatment group. Use the worst-case intensity per TEAE per subject, selecting only the TEAEs that were treatment-related (see section 12.1.2).

Population: safety.

Table to be created for the Week 12 interim analysis as well.

Table 14.3.1.12: Treatment-emergent adverse events up to Week 12: Tabulation of the drug-relatedness of serious events

Cross-tabulation of TEAE preferred terms versus their drug-relatedness; per body class and per treatment group. Selecting only the treatment-emergent serious adverse events.

Population: safety.

Table to be created for the Week 12 interim analysis as well.

Table 14.3.1.13: Treatment-emergent adverse events up to Week 12: Tabulation of the drug-relatedness of events leading to discontinuation

Cross-tabulation of TEAE preferred terms versus their drug-relatedness; per body class and per treatment group. Selecting only the TEAEs for which the study treatment was permanently discontinued (AE page), or for which the study was discontinued (trial termination page).

Population: safety.

Table to be created for the Week 12 interim analysis as well.

Table 14.3.1.14: Treatment-emergent adverse events up to Week 12: Tabulation of the drug-relatedness of events leading to a temporary stop

Cross-tabulation of TEAE preferred terms versus their drug-relatedness; per body class and per treatment group. Selecting only the TEAEs for which the study treatment was temporarily stopped (AE page).

Population: safety.

Table 14.3.1.15: Treatment-emergent adverse events up to Week 12: Tabulation of the drug-relatedness of individual stopping rules

Cross-tabulation of TEAE preferred terms versus their drug-relatedness; per body class and per treatment group. Selecting only the TEAEs that were flagged as “stopping criterion” in the eCRF by the investigator.

Population: safety.

